### 6.15.3 Vital Signs

Descriptive statistics for observed values and changes from baseline in the following vital signs will be presented by treatment group and visit:

- Systolic blood pressure (mmHg)
- Diastolic blood pressure (mmHg)
- Pulse rate (bpm)
- Respiration rate (breath / min)
- Body weight (kg)
- Body temperature (degrees Celsius)
- SpO2 (%)

Vital Signs log will be collected every 12 hours during study days 1-21. When study day has more than one record then summary table will use the average within the day.

Data for body temperature and SpO2 log will be presented in plot where individual subjects will be overlaid in one figure (spaghetti plot) by treatment group.

All vital sign data will be listed.

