8.2 Enrollment

Enrollment should be done after the subject has completed the screening assessments and after it has been determined that the subject meets all the inclusion and exclusion criteria.

Subject will be randomized into one of two treatment groups.

8.3 Day 1

The Day 1 visit assessments will serve as the baseline assessments.

- 1. The medical history should be reviewed and updated to include any changes occurring since the screening visit. This will include the following:
 - a. Number of days from onset of COVID-19 symptoms to Day 1

- b. Specific reason for hospitalization
- 2. Assessment of eligibility
- 3. Vital signs (temperature/pulse/supine, if possible, blood pressure)
- 4. SpO_2
- 5. Physical examination (including weight)
- 6. Chest X-ray or Computed Tomography (CT) scan
- 7. Clinical Laboratory Tests
 - a. Hematology (Appendix A)
 - b. Serum chemistry (Appendix A)
 - c. Urinalysis
- 8. Record the usage of any concomitant medications and ongoing treatments.
- 9. Adverse events (ongoing on Day 1)
- 10. First dose of study drug
- 11. Temperature and SpO₂ every 12 hours after dosing

8.4 Day 2 through Day 21

The following assessments will be conducted on each of Day 2 to Day 21

- 1. Temperature and SpO₂ every 12 hours
- 2. Vital signs (temperature/pulse/supine, if possible, blood pressure)
- 3. Record the usage of any concomitant medications and ongoing treatments. This should include the following:
 - a. Documentation of the standard of care
 - b. The clinical rationale for initiation of mechanical ventilation, if necessary
 - c. Documentation of supportive measures for ARDS (e.g., proning, paralytics, etc.)
 - d. Care decisions that are based on limitations of resources at the clinical site
- 4. Adverse events
- 5. Dose study drug
- 6. At the time of discharge from the hospital, patients should be advised to use refrain from prolonged exposure to the sun or use at least SPF 50 on all exposed skin and protective clothing during prolonged sun exposure until the Day 60 adverse event assessment.

8.5 Day 3, Day 9, and Day 15

The following additional assessment will be conducted on Days 3, Day 9 and 15:

- 1. Serum Chemistry (Appendix A)
- 2. Hematology (Appendix A)
- 3. Assessment of primary and secondary endpoints (Day 15 only)
- 4. Physical examination (including weight) (Day 15 only)
- 5. 12 lead ECG (single) (Day 15 only)
- 6. Pregnancy test (Day 15 only)

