#### 6.2.1 Baseline

Baseline is defined as the last non-missing value (either scheduled, unscheduled or repeat) before the subject receives the first dose of study drug.

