# 6.12.2.3 Proportion of subjects with normalization of fever and oxygen saturation through Day 15, Day 22, and Day 29.

The percentage of subjects with normalization of fever and oxygen saturation through Day 15, Day 22 and Day 29 (inclusive) will be summarized. A subject will be considered as a treatment success if fever normalization (body temperature < 37.0 °C) maintained for at least 24 hours AND peripheral capillary oxygen saturation (SpO2) >94% sustained for 24 hours is observed.

This analysis will compare the percentage of subjects that meet the composite endpoint at Day 15, Day 22, and Day 29.

Evaluation of the responder status will include all vital sign data and vital sign log data, and responder status will be evaluated at study days 15, 22 and 29 by checking if subject had normal temperature and SpO2 at least for the last 24 hours.

Responders are subjects who have fever normalization maintained for at least 24 hours AND peripheral capillary oxygen saturation (SpO2) >94% sustained for 24 hours is observed at the time of the visit.

Non-responders are subjects who died before the visit or do not meet both criteria of the endpoint (fever normalization and  $SpO_2>94\%$ ) at the time of the visit.

These endpoints will be analyzed using the same methodology as for the primary endpoint.

QMD Ref: Worldwide-TMP-ST-005-7.0 Effective: 12Aug2019 Governing QMD: Worldwide-SOP-ST-0		
Confidentiality Statement		
This document is the property of Worldwide Clinical Trials Inc. and may not be duplicated, copied, altered or removed from company without prior approval from Worldwide Quality Assurance or in compliance with Worldwide Standard Operating Procedures.		

Worldwide Clinical Trials Controlled Quality Management Document		
WORLDWIDE CLINICAL TRIALS	Sponsor:	Veru Inc.
	Protocol Number:	V0211901
STATISTICAL ANALYSIS PLAN. PHASE 2-3-4		

Separate analysis will be performed for each visit.

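### The vital-signs safety table uses daily means of SpO2 and temperature, which dilutes transient desaturation or fever and, read literally, mixes pre-dose and post-dose readings on Day 1

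*SAP*

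**What the plan says.** SAP 6.15.3 sets out three displays.

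- **Table.** "Descriptive statistics for observed values and changes from baseline in the following vital signs will be presented by treatment group and visit". SpO2 and body temperature are among the variables. The section adds "Vital Signs log will be collected every 12 hours during study days 1-21" and then "When study day has more than one record then summary table will use the average within the day".
- **Plot.** For the temperature and SpO2 log, "individual subjects will be overlaid in one figure (spaghetti plot) by treatment group".
- **Listing.** "All vital sign data will be listed".

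The list of outputs in SAP section 11 has a single vital-signs table, 14.3.6.1.1, of descriptive statistics. It has no shift, threshold or worst-value table for vital signs.

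On Day 1, Protocol 8.3 lists vital signs and SpO2, then the first dose, then temperature and SpO2 "every 12 hours after dosing". SAP 6.2.1 says: "Baseline is defined as the last non-missing value (either scheduled, unscheduled or repeat) before the subject receives the first dose of study drug". The averaging rule in 6.15.3 makes no exception for Day 1.

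**The concern.** For SpO2 and temperature, the safety question is usually how bad the worst reading was. Averaging two readings pulls the worst one halfway towards the other before any summary is made. The minimum and maximum in the table are then taken over daily means, so they cannot recover the reading that was lost. The trial enrols patients at high risk of ARDS whose SpO2 was 94% or lower at entry, so short desaturations are what a reader of this table would look for.

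The SAP takes a different line elsewhere. ECG and physical examination are shifted from baseline to the worst post-baseline record (6.15.4, 6.15.5), and each laboratory measurement is classed against its normal range, with shift tables (6.15.2). Vital signs have nothing comparable.

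On Day 1 the same rule may place a pre-dose reading and post-dose readings in one average. That would understate any early change.

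**Working it through.** No figure in the plan depends on this rule, so there is none to reproduce. All reading values below are assumed, because the documents give no data.

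**1. What averaging does to one excursion.** With two readings, mean = other − (other − low)/2, so the excursion is halved.

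- SpO2 88 and 98: (88 + 98)/2 = 93.0
- SpO2 90 and 98: 94.0
- SpO2 90 and 99: 94.5
- Temperature 38.0 and 36.5: (38.0 + 36.5)/2 = 37.25
- Temperature 37.4 and 36.5: 36.95

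Protocol 8.4 lists temperature both in the 12-hourly readings and in the daily vital signs. If the latter counts as a third record, the excursion shrinks to a third: 38.0, 36.4 and 36.4 give 36.93.

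**2. When the mean would look normal.** SAP 6.12.2.3 uses limits of >94% for SpO2 and <37.0 °C. The safety table does not apply them; they serve here only as a yardstick.

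- SpO2, two readings: the mean exceeds 94 only if low > 188 − other. With the other reading at 96, 98 or 100, the low one must be above 92, 90 or 88. A reading of 88 or lower can never average above 94.
- Temperature, two readings: the mean is below 37.0 only if high < 74 − other. With the other at 36.0, 36.5 or 36.8, the high one must be below 38.0, 37.5 or 37.2.

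So only moderate excursions cross the yardstick, but every excursion is diluted.

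**3. Average dilution.** For two normal readings with SD s and correlation r, the expected gap between mean and minimum is s × √((1 − r)/π).

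| | s = 2 | s = 3 | s = 4 |
|---|---|---|---|
| r = 0 | 1.13 | 1.69 | 2.26 |
| r = 0.5 | 0.80 | 1.20 | 1.60 |

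Capping SpO2 at 100%, with a patient mean of 95%, lowers the top independent value to about 2.1.

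**4. Share of low days that average above 94%.** This was simulated with 2,000,000 days per setting, two readings a day rounded and capped at 100, and s = 2 to 4. Among days with a reading of 92% or lower:

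| Patient mean | r | Share with daily mean >94% |
|---|---|---|
| 94% | 0 | 8-17% |
| 95% | 0 | 18-24% |
| 96% | 0 | 33-35% |
| 95% | 0.3 | 8-17% |
| 95% | 0.5 | 3-12% |
| 95% | 0.7 | 1-6% |

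For days with a reading of 90% or lower, at mean 95%, the share is 3-11% at r = 0 and 0-2% at r = 0.5.

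**5. Day 1.** Take a pre-dose SpO2 of 90 and one post-dose reading of 96. Baseline under 6.2.1 is 90 and the true change is 96 − 90 = +6. The pooled Day 1 mean is (90 + 96)/2 = 93, so the table shows +3. With two post-dose readings of 96 it is (90 + 96 + 96)/3 = 94, shown as +4.

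**6. Worst value over the whole of Days 1-21.** A subject observed for 5 days gives 10 readings; one observed for 21 days gives 42. The expected minimum of 42 independent normal readings is 0.64 SD below that of 10. At SD 2 to 4 that is 0.64 × 2 = 1.3 to 0.64 × 4 = 2.6 points, at least as large as the dilution in step 3, and it comes from length of observation alone.

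**The case against.** The strongest case against is that averaging repeated readings for a by-visit descriptive table is an ordinary choice. The table carries no test, in a proof-of-concept trial of about 40 subjects, and raw values appear in the individual plots and the listing. Important desaturation can also surface as an adverse event tabulated by maximum grade (6.15.1) or in the oxygen-use shifts (6.12.3.2). All of this bears on how much the point matters. It does not close the gap: plots and listings give no count by arm, adverse events depend on being reported, and oxygen use measures treatment rather than saturation.

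Four stronger readings are tempting, and the documents do not support them.

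- **That excursions are cancelled.** Two readings halve an excursion, and severe ones remain visible as abnormal means.
- **That subjects are misclassified against 94% or 37.0 °C.** Those limits belong to the endpoint in 6.12.2.3. The safety table has no threshold row, so steps 2 and 4 show only how normal a day might look.
- **That baseline is contaminated.** SAP 6.2.1 fixes it as the last pre-dose value, and nothing in 6.15.3 overrides that. The SAP also does not say whether the pre-dose visit record and the post-dose log are pooled, so the Day 1 issue is unclear wording with a literal reading that does harm.
- **That this is the only comparison of SpO2 and temperature by arm during Days 1-21.** Tables 14.2.3.1 and 14.2.3.2 compare fever and SpO2 status by arm at Day 15 from unaveraged readings, where the criterion is that normal values "sustained for 24 hours is observed". That endpoint looks back only over the last 24 hours at Days 15, 22 and 29, so a desaturation on Day 5 does not enter it.

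**Conclusion.** The point holds as a limited weakness in a descriptive safety display. The one vital-signs table dilutes transient SpO2 and temperature excursions, by half with two readings a day, and no other planned table by arm gives a worst vital-sign value. The average gap between daily mean and daily minimum is about 1.1 to 2.1 SpO2 points for independent readings with SD 2 to 4 and patient mean 95%, and smaller if readings 12 hours apart are correlated. The share of low days that average above 94% is 18-24% under independence at that mean and about 3-17% at correlations of 0.3 to 0.5. These sizes rest on assumed means, SDs and correlations; the halving does not.

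The Day 1 row needs a clarifying sentence, because a literal reading shrinks that day's change. Neither issue touches baseline as defined in 6.2.1, the fever/SpO2 endpoint or the primary analysis.

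**What to change.** In SAP 6.15.3:

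1. Keep the daily mean. Add, for each study day and arm, summaries of each subject's lowest SpO2 and highest temperature from the scheduled 12-hourly readings, with the number of subjects observed that day. Using scheduled readings only stops extra readings from pushing the daily extreme further out.
2. State that baseline is the last pre-dose value (6.2.1) and that the Day 1 post-baseline row uses post-dose readings only.
3. If an overall worst-value row is wanted, use a fixed early window or show it beside the number of days observed. A minimum over all of Days 1-21 depends on how long the subject was observed, which (assuming the 12-hourly log stops at discharge or death) is itself an outcome and could differ by arm.

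The cost is SAP wording and one derivation on data already collected. The downsides are more table rows, and daily extremes that are slightly noisier than daily means.

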# 6.15.4 Physical Examination

Shift tables for each body system from baseline to worst post-baseline record will be presented (Normal, Abnormal NCS and Abnormal CS). NCS = Abnormal Not Clinically Significant, CS = Clinically Significant.

All physical examination data will be listed.

# 6.15.5 Electrocardiogram Data

Descriptive statistics for observed values and changes from baseline in the following ECG variables will be tabulated at each follow-up visit:

- Heart rate (bpm)
- PR interval (ms)

QMD Ref: Worldwide-TMP-ST-005-7.0 Effective: 12Aug2019	Governing QMD: Worldwide-SOP-ST-001	
Confidentiality Statement		
This document is the property of Worldwide Clinical Trials Inc. and may not be duplicated, copied, altered or removed from company without		
prior approval from Worldwide Quality Assurance or in compliance with Worldwide Standard Operating Procedures.		

Worldwide Clinical Trials Controlled Quality Management Document		
WORLDWIDE CLINICAL TRIALS	Sponsor:	Veru Inc.
	Protocol Number:	V0211901
STATISTICAL ANALYSIS PLAN. PHASE 2-3-4		

- RR interval (ms)
- QRS duration (ms)
- QT interval (ms)
- QTc interval (ms)
- QTc interval (ms) [Bazett's formula QTcB]
- QTc interval (ms) [Fridericia's formula QTcF]

Shift tables in relation to the overall interpretation (Normal, Abnormal NCS and Abnormal CS) from baseline to worst post-baseline record will be presented.

All ECG data will be listed.

### 6.15.6 Chest X-Ray / Computed Tomography (CT)

Shift tables for chest X-ray / CT from baseline to each timepoint will be presented (Normal, Abnormal).

All chest X-ray / CT data will be listed.

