 Plasma samples for pharmacokinetic assessment will be taken at baseline (prior to dosing on Day 15) and at 4 hours (±2 hours), 12 hours (±2 hours) after dosing on Day 15, and at 24 hours (±2 hours) after dosing on Day 15 (prior to dosing on Day 16). (Day 15 only)

8.6 Day 22 ± 3 days (these assessments will also be done at Early Termination or Discontinuation from the study)

The following assessments will be performed on Day 22 (\pm 3 days):

- 1. Vital Signs (temperature/pulse/supine blood pressure)
- 2. SpO₂
- 3. Physical examination (including weight)
- 4. 12-lead ECG (single)
- 5. Chest X-ray or CT scan
- 6. Clinical Laboratory tests
 - a. Hematology (Appendix A)
 - b. Serum chemistry (Appendix A)
 - c. Urinalysis
- 7. Adverse events
- 8. Record the usage of any concomitant medications and ongoing treatments.
- 9. Assessment of primary and secondary endpoints

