12.2 Appendix B: Schedule of Study Evaluations

Day	Screen ^a	Day 1	Days 2-21	Days 3, 9, & 15	Day 16	Days 22 ^d and 29	Days 45 and 60
Informed Consent and	Х						
HIPAA							
Medical History	Х	Х					
Assessment of Eligibility	Х	Х					
Physical Exam	Х	Х		Xf		Х	
Vital signs	Х	Х	Х			Х	
Pregnancy test (female	Х		Xf			X ^g	
subjects only)				0			
12-lead ECG (single)	Х			X ^t		X	
Chest X-ray or CT		Х				Х	
Clinical Laboratory Tests							
Hematology	Х	Х		Х		Х	
Urinalysis	Х	Х				Х	
Serum Chemistry	Х	Х		Х		Х	
Temperature/SpO ₂	Х	Х	Xe			Х	
Dosing ^{b,c}		Х	Х				
Pharmacokinetic assessment				X ^{h, f}	X ^h		
Assessment of primary and secondary efficacy endpoints				\mathbf{X}^{f}		Х	Х
Assessment of conmeds	Х	Х	Х			Х	
Assessment of AEs		Х	Х			Х	X

a Screening evaluations are to be conducted within 2 days prior to Day 1.

b Subjects will be treated for 21 days OR until discharged from hospital

c Subjects can be discontinued if they are not responding to therapy d Early termination assessments the same as Day 22 assessments

e Temperature and SpO₂ will be taken every 12 hours on these days

f Day 15 only g Day 29 only

h Plasma samples for pharmacokinetic assessment will be taken at baseline (prior to dosing on Day 15) and at 4 hours (±2 hours), 12 hours (±2 hours) after dosing on Day 15, and at 24 hours (±2 hours) after dosing on Day 15 (prior to dosing on Day 16).

PROTOCOL SIGNATURE PAGE

Protocol Number:	V0211901
Protocol Date:	FINAL Amendment 6 (Version 7)/ 25 September 2020
Protocol Title:	Randomized, Placebo-Controlled, Phase 2 Study of VERU-111 for the Treatment of Severe Acute Respiratory Syndrome Coronavirus 2 (SARS-CoV-2) in Patients at High Risk for Acute Respiratory Distress Syndrome (ARDS).

SIGNATURE:

Sponsor

Date

Name and Title of Sponsor Representative

This signature of the Sponsor Representative constitutes approval of this protocol.

PRINCIPAL INVESTIGATOR SIGNATURE PAGE

Protocol Number:	V0211901
Protocol Title:	Randomized, Placebo-Controlled, Phase 2 Study of VERU-111 for the Treatment of Severe Acute Respiratory Syndrome Coronavirus 2 (SARS-CoV-2) in Patients at High Risk for Acute Respiratory Distress Syndrome (ARDS).
Protocol Date:	FINAL Amendment 6 (Version 7)/ 25 September 2020

SIGNATURE:

Principal Investigator:

Date

Name of Principal Investigator (Please Print)

Address of Principal Investigator

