#### 5 RANDOMIZATION

Approximately, 40 subjects are planned to be randomized at a 1:1 ratio into two treatment arms (20 subjects in the VERU-111 treated group and 20 subjects in the Placebo treated group).

The subjects with documented evidence of COVID-19 infection (by standard diagnostic method) with symptoms for less than 8 days will be enrolled. Subjects will be at high risk for the development of ARDS.

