#### STATISTICAL ANALYSIS PLAN. PHASE 2-3-4

Table Number	Table Title	Included in Preliminary Analysis	Included in DSMB (Table	Validation Method	Shell Number (if
142111	O HC CAL E (ITTD 14')		No.)	ID	repeat)
14.3.1.1.1	Overall Summary of Adverse Events (ITT Population)		Yes (S6)	IP	
14.3.1.2.1	TEAEs by System Organ Class and Preferred Term (ITT Population)		Yes (S7)	IP	
14.3.1.2.2	Treatment-Related TEAEs by System Organ Class and Preferred Term (ITT Population)		Yes (S8)	IP	14.3.1.2.1
14.3.1.2.3	Serious TEAEs by System Organ Class and Preferred Term (ITT Population)		Yes (S9)	IP	14.3.1.2.1
14.3.1.2.4	Treatment-Related Serious TEAEs by System Organ Class and Preferred Term (ITT Population)		Yes (S10)	IP	14.3.1.2.1
14.3.1.3.1	TEAEs by System Organ Class, Preferred Term and Maximum Toxicity Grade (ITT Population)			IP	
14.3.1.3.2	TEAEs by System Organ Class, Preferred Term and Strongest Relationship to Study Treatment (ITT Population)			IP	14.3.1.3.1
14.3.2	Listings of Deaths, Other Serious and Significant Adverse Events				
14.3.2.1	Listing of Deaths (ITT Population)		Yes (S11)	IP	
14.3.2.2	Listing of Serious TEAEs (ITT Population)			IP	14.3.2.1
14.3.3	Narratives of Deaths, Other Serious and Certain Other Significant Adverse Events				
	Not applicable				
14.3.4	Abnormal Laboratory Values				
14.3.4.1	Listing of Abnormal Laboratory Values (ITT Population)			IP	
14.3.5	Laboratory Data				
14.3.5.1.1	Hematology Descriptive Statistics (ITT Population)		Yes (S12)	IP	14.2.2.1
14.3.5.1.2	Hematology Shift Table (ITT Population)			IP	
14.3.5.2.1	Chemistry Descriptive Statistics (Safety Population)		Yes (S13)	IP	14.2.2.1
14.3.5.2.2	Chemistry Shift Table (ITT Population)			IP	14.3.5.1.2
14.3.5.3.1	Urinalysis Descriptive Statistics (Continuous) (ITT Population)		Yes (S14)	IP	14.2.2.1
14.3.5.3.2	Urinalysis Descriptive Statistics (Categorical) (ITT Population)		Yes (S15)	IP	
14.3.5.3.3	Urinalysis Shift Table (ITT Population)			IP	14.3.5.1.2
14.3.6	Vital Signs				
14.3.6.1.1	Vital Signs Descriptive Statistics (ITT Population)			IP	14.2.2.1
14.3.7	Physical Examination				
14.3.7.1.1	Physical Examination Shift Table (ITT Population)			IP	14.3.5.1.2
14.3.8	ECG				
14.3.8.1.1	ECG Descriptive Statistics (ITT Population)			IP	14.2.2.1
14.3.8.1.2	ECG Shift Table (ITT Population)			IP	14.3.5.1.2
14.3.9	Other Safety				
14.3.9.1.1	Chest X-Ray / CT Shift Table (ITT Population)			IP	14.3.5.1.2
14.4	Pharmacokinetics				

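### The chest imaging shift table pools X-ray and CT with no same-modality rule, so in a subject who switches, a difference in detection can be reported as a change in the lungs

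*SAP*

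**What the plan says.** **Protocol.** The Day 1 assessments (section 8.3), which serve as baseline, include "Chest X-ray or Computed Tomography (CT) scan". Day 22, also used for early termination (section 8.6), and Day 29 (section 8.7) each include "Chest X-ray or CT scan". The schedule in Appendix B has one row, "Chest X-ray or CT", and no footnote ties the follow-up modality to the one used at baseline.

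**SAP.** Section 6.15.6 specifies one analysis: "Shift tables for chest X-ray / CT from baseline to each timepoint will be presented (Normal, Abnormal". The list of outputs has a single table for it, 14.3.9.1.1, titled "Chest X-Ray / CT Shift Table (ITT Population". The general baseline rule in section 6.2.1 sets no condition on modality: "Baseline is defined as the last non-missing value (either scheduled, unscheduled or repeat) before the subject receives the first dose of study drug". The only other provision is "All chest X-ray / CT data will be listed". Nothing in the SAP pairs like with like, stratifies by modality, or flags a subject whose modality changed.

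**The concern.** X-ray and CT need not detect the same findings. If a subject's lungs are abnormal and unchanged, a baseline CT read as abnormal followed by an X-ray read as normal enters the table as recovery. The reverse order enters it as worsening. A pooled two-category table cannot separate such a subject from one whose lungs really changed.

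Two features of the SAP make the gap visible. For local laboratory data, section 6.15.2 requires units to be harmonised before tabulation and uses each laboratory's own normal range; imaging has no comparable step. The physical examination and ECG shifts (6.15.4, 6.15.5) split abnormal results by clinical significance, whereas imaging has only two categories. A minor finding visible on one modality alone therefore counts as a full shift.

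What is at stake is the reading of the only planned imaging summary, in a trial of subjects at high risk of ARDS. No efficacy conclusion depends on it.

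**Working it through.** The plan states no figure on this point and has no power calculation (SAP section 4), so there is nothing to reproduce. The check has two parts: what the text permits, and how large the artefact could be under stated assumptions.

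**1. What the text permits.** Either modality is allowed at all three imaging visits, no rule requires the same one, and one table pools both. A switched pair can therefore enter the table as an ordinary shift.

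**2. Inputs for scale**
- Subjects per arm: 20. SAP section 5 says "Approximately, 40 subjects are planned to be randomized at a 1:1 ratio into two treatment arms".
- Detection of an unchanged abnormality: X-ray (Se_X) 0.60 to 0.80, CT (Se_CT) 0.90 to 0.97. These are assumptions; the documents give none.
- Share of subjects who switch: 25%, also an assumption.

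**3. Net false shift in a switched subject with unchanged abnormal lungs**

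Net = Se_CT − Se_X, whatever the dependence between the two readings.
- Smallest: 0.90 − 0.80 = 0.10
- Largest: 0.97 − 0.60 = 0.37

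From X-ray to CT the net movement is towards Abnormal; from CT to X-ray it is towards Normal. A same-modality pair has an expected net of zero.

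**4. Subjects per arm per visit**

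Switched subjects: 0.25 × 20 = 5.
- 5 × 0.10 = 0.5
- 5 × 0.37 = 1.85, about 1.9

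This takes all five to switch in the same direction, to have unchanged abnormal lungs and to be imaged at that visit.

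**5. Why the net, not the gross, figure**

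If readings are independent, the chance that an X-ray-to-CT pair moves from Normal to Abnormal is (1 − Se_X) × Se_CT. That runs from 0.2 × 0.90 = 0.18 to 0.4 × 0.97 = 0.39. Part of this is reading noise, which same-modality pairs share:

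| Pair | Total discordance under independence | Se_X = 0.80 | Se_X = 0.60 |
|---|---|---|---|
| X-ray and CT | (1 − Se_X)Se_CT + Se_X(1 − Se_CT) | 22-26% | 41-42% |
| X-ray and X-ray | 2 × Se_X(1 − Se_X) | 32% | 48% |

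Under that model, repeat X-ray disagrees more often in total than a mixed pair does. Only the net 10 to 37 points is specific to changing modality.

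**6. A second illustration with different inputs**

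Let f be the share switching from CT to X-ray, and g the chance that X-ray reads Normal when CT read Abnormal and the lungs are unchanged. Expected false shifts per arm are 20 × f × g, and the chance of at least one is 1 − (1 − f × g)^20. Both f and g are assumptions.
- f = 10%, g = 0.05: 0.1 expected; 9.5% chance of at least one
- f = 25%, g = 0.20: 1.0 expected; 64%
- f = 50%, g = 0.30: 3.0 expected; 96%
- f = 0: zero

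If switching were 10% in one arm and 40% in the other, the spurious difference between arms would be g × (0.40 − 0.10): 3 points at g = 0.10 and 9 points at g = 0.30.

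**The case against.** The strongest reply is that little depends on this table. It is an untested safety display, and imaging enters neither the primary nor any secondary endpoint. Lung outcome is measured by respiratory failure, the WHO scale, oxygen saturation and ventilation days, with oxygen-use shifts as an exploratory output. All of that stands and sets the weight of the point.

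The existing provisions may also help. All imaging data will be listed, SAP section 6 allows further tables if the data warrant them, and the shell for 14.3.9.1.1 (a repeat of 14.3.5.1.2) is not in the documents, so a split by modality there cannot be excluded. This stands in part. The listing might let a reader find switched subjects if it shows modality, but it would not correct the table, and the SAP text specifies no split.

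A reader might infer that the table is biased between arms, on the argument that the arm discharged sooner would be imaged differently at Days 22 and 29. The documents do not support this. No section links modality to care setting or arm, and earlier discharge in one arm is itself a supposition. A reader might also infer that changes of instrument will in fact appear as lung changes. The documents do not show that any subject switches, so the most that can be said is that they can.

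**Conclusion.** The point holds as a minor one. The plan permits a change of modality within a subject and pools the modalities in one shift table, so a detection difference can be counted as a change in the lungs.

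Its size cannot be fixed from the documents. The 10 to 37 points rest entirely on assumed detection rates. The 0.5 to 1.9 subjects per arm rest also on an assumed 25% switching, all in one direction, in subjects with unchanged abnormal lungs. The 18% to 39% gross range should not be taken as the effect of switching, because it includes reading noise that same-modality pairs also carry. A difference between arms remains possible, but only if switching differs by arm.

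**What to change.** In SAP 6.15.6 and table 14.3.9.1.1, keep all subjects and present the shift by modality pair: X-ray to X-ray, CT to CT, and switched. Give counts by arm, with the direction of the switch for the last group. State that the imaging listing (16.2.8.8) shows the modality of each image.

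Switched subjects should not be excluded. Modality at follow-up is determined after randomisation, so a table restricted to same-modality pairs would select on something that could differ by arm.

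No request to sites is proposed. SAP section 9 says all randomised subjects had been treated, so Day 1 imaging is presumably past, and asking sites to repeat a modality would add a procedural demand that the analysis does not need.

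The cost is a longer descriptive table with small cells. It needs no new procedure and no change to any efficacy analysis.
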